1.0 Introduction and Background

1.1 Synopsis

Approximately half of the 1.7 million new cancer diagnoses annually will be treated with ionizing radiation therapy (RT). Improvements in screening and treatment continue to decrease mortality. As a result, long term sequelae of therapy have become a major concern¹⁻³.

Thoracic stereotactic body radiation therapy (SBRT) for the treatment of primary or metastatic lung tumors near the chest wall unavoidably delivers high doses of radiation to the surrounding normal ribs or vertebrae and can predispose patients to significant chest wall pain (CWP), radiation induced rib fractures (RIRF) or even vertebral fractures⁴⁻⁶. Rates of toxicity have been correlated with dose received by the chest wall. On average, around 35% of patients develop grade 3 or higher CWP when greater than 30 cc of chest wall receives 30 Gy or more⁷.

In clinical practice this is a very common scenario and a difficult dosimetric constraint to achieve. The incidence of rib fractures within the first year of treatment has been reported as high as 40%^{6,8-13}. Patients can experience severe pain, compromised ventilation, and impaired quality of life. In the elderly, decreased oxygen saturation as a result of compromised ventilation can reduce life expectancy¹⁴. Radiation related bone injury is not limited to the ribs and SBRT however. Rather, it is a source of morbidity at multiple skeletal locations. The five year post-RT pelvic fracture rate is ~30% in women treated for the most common gynecologic malignancy, endometrial adenocarcinoma^{15,16}. Likewise, hazard ratios for RT induced hip and femoral neck fracture indicate significant increased risk at five years post-RT for cervical (1.66), rectal (1.65), and anal (3.16) cancers¹⁷. Alarmingly, the rate of incomplete healing is high with RT-induced fractures, which greatly contributes to morbidity^{18,19}. Therefore, RT-induced bone damage is a persistent and major source of functional impairment, pain, and mortality in many cancer survivors.

The exact mechanisms of RT-induced bone damage are unclear. Historically, persistent damage to osteoblasts was thought to play a role by lowering bone formation and bone mineral density over time²⁰⁻²³. However, we recently discovered that local RT rapidly increases the number and activity of osteoclasts in rodents²⁴, and we have shown this burst of osteoclast activity causes substantial early bone loss²². This is now well-accepted²⁵⁻³². By suppressing osteoclast activity during RT using an antiresorptive bisphosphonate, risedronate, we prevented this rapid bone loss in rodents²². This is illustrated in Fig. 1 and Fig. 2. Suppressing early osteoclast activity is an appealing therapeutic approach for preventing RT-induced fractures. A variety of urinary biomarkers have been linked to increased osteoclastic activity in osteoporotic populations, and the most frequently tested marker is urinary NTX N-telopeptide³³. These biomarkers have been assessed following radiation to the pelvis with or without bisphosphonates and were shown to decrease with the addition of bisphosphonates³⁴.

We have devised a novel 3D mapping approach which utilizes DICOM computed tomography (CT) images and allows us to visualize and quantify the changes in bone cortical thickness (C.Th) following RT and associate bone changes with RT dose distribution. (Fig. 3) Furthermore, we illustrated dose-dependent cortical thinning to the exact sites of eventual fracture in patients receiving lung SBRT near the chest wall, as well as bone loss to discrete, weight-bearing sub-regions of the femoral neck after RT for pelvic cancers^{4,35}. In areas of the ribs receiving > 30 Gy approximately 92% of treated patients developed significant cortical thinning by 3 months, and 2 patients developed rib fractures by as early as 6 months³³. Using this mapping technique, we have also illustrated significant and persistent cortical thickness changes as early as 2 months post treatment in the treated vertebrae of nonhuman primates receiving single fraction high dose chest RT (Fig. 4)³⁶.

Clinical relevance

On review of treatment planning records over the last month in our department, we have treated 18 patients who would have qualified for inclusion on this study. This is a reasonable representation of our average SBRT treatment population. More than 2/3 of our SBRT plans unavoidably exceed standardized dosimetry constraints for the ribs/chest wall, and roughly 30-40% of our patient population complains of chest wall pain requiring narcotics/analgesics after SBRT. Typically this occurs within 3 - 8 months. This presents clinicians with a difficult decision to either compromise on effective tumor dose by reducing the dose per fraction, or accept a higher risk of chest wall toxicity with more intensive fractionations proven to have better local tumor control.

Conclusions:

We aim to determine if single dose prophylactic suppression of early RT induced osteoclast activity with bisphosphonates diminishes or prevents RT induced cortical bone thinning, fracture, and pain.

[figure not shown]

Figure 1. MicroCT images are shown of trabecular bone in the proximal tibial metaphysis (Tibia) and distal femoral metaphysis (Femur) from mice that were non-irradiated (No IR) and those who were irradiated (IR) then sacrificed 1 week later. In the irradiated mice, a 2 Gy dose of x-rays was administered with a PBS placebo injected subcutaneously (IR+ Placebo) or with subcutaneous risedronate injections (IR+ Risedronate).

[figure not shown]

Figure 2. Trabecular number vs time in mice. The blue boxes represent mice that were not irradiated and were given a PBS placebo injected subcutaneously (No IR +Placebo), while the red triangles and green circles represent mice that received a 2 Gy dose of x-rays was administered with a PBS placebo injected subcutaneously (IR+ Placebo) or with subcutaneous risedronate injections (IR+ Risedronate).

[figure not shown]

Figure 3. A) Illustration of cortical thickness vector measurement for a rib. (B) This is performed thousands of times on each CT scan to create cortical thickness maps for all ribs with a color scale corresponding to thickness in millimeters. (C) Radiation dose is associated with locations showing rib thinning. (D) Cortical thinning and subsequent rib fracture is visually evident at 3 and 6 months post SBRT in an area of chest wall that received nearly the tumor prescription dose (square box).

[figure not shown]

Figure 4. A) Non-human primate rhesus monkeys received a single fraction 10 Gy to the whole chest, and isodose curves illustrating radiation dose distribution are shown. B) Cortical thickness maps illustrated dose dependent cortical thickness loss at 2 months post radiation.

1.2 Risedronate Background Information

Much of the following detailed information below was obtained from the product monograph from Allegran Pharma Co. Markham, Ontario L6G0B5 August 2017, Submission Control 205107. In some instances, this information was directly reproduced from the product monograph.

Background information on the study agent:

ACTONEL® (risedronate sodium hemi-pentahydrate) is a commonly used bisphosphonate medication that is FDA approved for the indications below.

- Treatment and prevention of osteoporosis in postmenopausal women
- Treatment of osteoporosis in men, to improve bone mineral density
- Treatment and prevention of glucocorticoid-induced osteoporosis in men and women
- Paget's disease of bone

Clinical studies and use with radiation

Risedronate has been utilized in multiple large prospective clinical trials and was shown to significantly reduce vertebral fracture incidence in patients with low bone mass and vertebral fractures, regardless of age, years since menopause or disease severity at baseline. A North American trial illustrated a significant reduction in the 1-year rate of new vertebral fractures by 65% compared to placebo. Similarly, a multinational trial also illustrated a 61% reduction in the 1-year rate of new vertebral fractures.

There are no contraindications to concurrent use of risedronate and chest external beam radiation. Bisphosphonates are not routinely discontinued during SBRT for lung tumors. There is a known risk of jaw osteonecrosis that may occur following dental surgery or spontaneously with bisphosphonates, however this is not a reported finding in the ribs. Osteoradionecrosis in the jaw is a separate process

that can occur when treating head and neck cancers without bisphosphonates and is a result of poor vasculature in the mandible. In the setting of head and neck cancer treatment with radiotherapy, we would discontinue bisphosphonates, however this is not extrapolated to other parts of the body when receiving radiotherapy while on bisphosphonates

Clinical studies have been performed with concurrent use of bisphosphonates and radiation therapy in the pelvis without excess toxicity. Choo et al, conducted a randomized trial in patients with prostate cancer receiving placebo or risedronate concurrently with external beam radiation and androgen deprivation therapy³⁷. They illustrated prevention of bone mineral density (BMD) loss at 2 years and significant suppression of bone turnover biomarkers in patients receiving risedronate. There were no excess or unexpected toxicities due to concurrent risedronate and RT.

Similarly, Gierloff et al. illustrated that the addition of zolendronate with radiation in patients with metastatic bone disease, prevented early radiation induced bone collagen degradation when compared to placebo³⁴. There was significant reduction in urine excretion markers of degradation including hydroxylsypyridinoline and lysylpyridinoline. Again, no excess toxicity was noted with the concurrent use of bisphosphonates and radiation.

Pharmacokinetics:

Summary of Pharmacokinetic Parameters of Risedronate						
	C _{max} (ng/mL)	t _{max} (h)	t _{1/2, Z} (h)	AUC _{0 - ∞} (ng h/mL)	Clearance (L/h/kg)	V _Z (L/kg)
5 mg tablet; single dose	0.85	0.93 ^a	206.1	3.45	19.94	5542
30 mg tablet; single dose	4.2	0.87 ^a	226.1	17.1	23.60	7542
35 mg tablet; multiple dose ^b , steady state	10.6	0.49	nd	53.3	12.9	nd
35 mg DR tablet; single dose	14.1	3.0 ^d	nd	34.2 ^e	nd	nd
150 mg tablet, single dose	74.8 ^d	0.66 ^d	349.6 ^d	332.4 ^d	6.94 ^d	3118 ^d

^a: arithmetic mean; ^b: administered weekly; ^c: administered on two consecutive days per month (150 mg total monthly dose); ^d: geometric mean; ^e: t_{1/2, Z} is the half-life of the terminal exponential phase; V_Z is the terminal volume of distribution uncorrected for bioavailability; nd: not determined; ^e AUClast.

Drug Interactions:

No specific drug-drug interaction studies were performed with risedronate sodium film-coated tablets. Animal studies have demonstrated that risedronate is highly concentrated in bone and is retained only minimally in soft tissue. No metabolites have been detected systemically or in bone. The binding of risedronate to plasma proteins in humans is low (24%), resulting in minimal potential for interference with the binding of other drugs. In an additional animal study, there was also no evidence of hepatic microsomal enzyme induction. In summary, risedronate sodium is not systemically metabolized, does not induce cytochrome P450 enzymes and has low protein binding. Risedronate sodium is therefore not expected to interact with other drugs based on the effects of protein binding displacement, enzyme induction or metabolism of other drugs. In vitro studies suggest that the amount of EDTA contained in the ACTONEL DR formulation (approximately 1.5 mM) will not significantly affect aqueous solubility of antivirals (nelfinavir, lamivudine, emtricitabine) and drugs with a narrow therapeutic index (digoxin, lithium carbonate, potassium chloride). Thus, co-administration with ACTONEL DR is not likely to alter their absorption.

Patients in clinical trials were exposed to a wide variety of commonly used concomitant medications (including NSAIDs, H2-blockers, proton pump inhibitors, antacids, calcium channel blockers, beta-blockers, thiazides, glucocorticoids, anticoagulants, anticonvulsants, cardiac glycosides). While there was no apparent evidence of clinically relevant interactions in the clinical trials, such interactions cannot be ruled out on the basis on these data.

Metabolism:

There is no evidence that risedronate is systemically metabolized.

Route of elimination:

Approximately half of the absorbed dose is excreted in urine within 24 hours, and 85% of an intravenous dose is recovered in the urine over 28 days. The mean renal clearance is 105 mL/min (CV = 34%) and mean total clearance is 122 mL/min (CV = 19%), with the difference primarily reflecting non-renal clearance or clearance due to adsorption to bone. The renal clearance is not concentration dependent, and there is a linear relationship between renal clearance and creatinine clearance. Unabsorbed drug is eliminated unchanged in feces. Once risedronate is absorbed, the serum concentration-time profile is multi-phasic with an initial half-life of about 1.5 hours and a terminal exponential half-life of 480 hours. Although the elimination rate of bisphosphonates from human bone is unknown, the 480 hour half-life is hypothesized to represent the dissociation of risedronate from the surface of bone.

Special Populations and Conditions

Pediatrics: Risedronate pharmacokinetics have not been studied in patients < 18 years of age.

Geriatrics: Bioavailability and disposition are similar in elderly (> 65 years of age) and younger subjects. No dosage adjustment is necessary.

Gender: Bioavailability/disposition following oral administration are similar in men and women.

2.0 Objectives

This is a double blind randomized controlled study investigating the efficacy of a single dose of 150 mg risedronate (a bone anti-resorptive) vs a single dose of placebo given prior to SBRT for peripheral lung tumors that are within 2 cm of the chest wall. Our hypothesis is that the use of a single dose of 150 mg risedronate will eliminate or greatly reduce the rapid bone loss that occurs with radiation induced early osteoclast recruitment/activation.

Patients will be given either a single dose of 150 mg risedronate or placebo at the time of their treatment mapping “simulation” CT scan or within 7-21 days of the start of SBRT. Typically, radiation treatments begin at 1 – 3 weeks following this mapping scan, as each treatment plan requires detailed physics calculations and quality assurance checks.

All CT imaging referenced below is performed as a routine standard of care surveillance and is necessary for cancer treatment follow-up. These chest CT scans that are utilized in this research protocol would be performed every 3 months regardless of inclusion on this trial.

2.1 Primary Objective(s)

2.1.1 The primary objective is to assess the percent change in bone mean cortical thickness within regions of bone receiving 30 Gy or more at 3 months after SBRT. The % change

in mean cortical thickness will be compared between patients who received risedronate and those who received placebo.

2.2 Secondary Objective(s)

- 2.2.1 In addition to the primary objective, we will further analyze the remaining routine follow-up chest CT scans, for mean cortical thickness change in regions of bone that received 0 – 10 Gy, >10 – 20 Gy, > 20 – 30 Gy, > 30 – 40 Gy, and > 40 Gy at all time points including 3 months, 6 months, 9 months, and 12 months. These scans are standard of care and would be performed regardless of inclusion on this trial. This will allow us to determine the potential persistence of effects from SBRT and bisphosphonate use.
- 2.2.2 We will assess and compare the incidence and grade (per modified CTCAE v.5) of radiation induced chest wall pain within the radiation treatment portal (within the 50% isodose line) at time of each routine follow up visit (3 months, 6 months, 9 months, and 12 months post SBRT). The purpose of utilizing a placebo and double-blind design is that chest wall pain is a subjective finding. Furthermore, it is unclear if chest wall pain from radiation is directly due to bone damage, nerve damage, muscle irritation, or a combination of all of these factors. The use of placebo will help us reduce the potential for bias in pain assessment.
- 2.2.3 We will assess and compare the incidence of rib and vertebral fractures (as noted on CT imaging) that occur within 12 months of irradiation and are within the radiation treatment field. The radiation treatment field will be defined as within the 50% isodose line.
- 2.2.4 The urine concentration of an osteoclast-specific biomarker, urinary N-telopeptide (NTX) indicating osteoclast activity will be assessed prior to SBRT and at each routine follow up visit (at 3 months, 6 months, 9 months, and 12 months post SBRT).

2.3 Exploratory Objectives

- 2.3.1 We will analyze novel anatomic dosimetric substructures on already completed radiation plans such as rib neurovascular bundles. These anatomical structures will be contoured onto the stored planning CT scans and the raystation planning system will allow us to calculate the dose that these structures received. We will assess the relation between this calculated dose and development of/grade of chest wall pain during follow-up. The standard structure that is routinely contoured for these cases is a crude ring encompassing 2-3 cm of the entire chest wall. We are hypothesizing that dose to specific substructures in the chest wall may be more useful in the prediction of chest wall pain development.
- 2.3.2 If funding permits, we will analyze, and compare between groups, the urine concentration of markers of bone turnover activity. These will all be assessed prior to SBRT and at the 6 month follow up visit post SBRT.
- 2.3.3 We will analyze and compare between groups the urine concentrations of pain-associated cytokines prior to SBRT and at the 6 month follow up visit post SBRT. Also, if funding permits, the urine concentration of pain-related neurotrophic growth factors (proNGF, proBDNF, GDNF), and neuropeptides (CGRP and Substance P) will be measured.

3.0 Patient Selection

Biopsy is not required for enrollment.

The lung tumor may be a lung primary tumor or a metastatic tumor to the lung.

Prior radiation to any part of the body including the lungs, breast, or thorax is permitted.

3.1 Inclusion Criteria

- 3.1.1 Patients must be 18 years or older, but there is no upper limit on age of inclusion.
- 3.1.2 Patients must have a peripheral lung tumor that is amenable to SBRT as determined by the treating radiation oncologist. To be classified as a peripheral lung tumor, the tumor edge (the edge of the gross tumor volume or GTV in radiation treatment planning software) must be within 2 cm of the chest wall. This is determined by the treating radiation oncologist. The chest wall is defined as the chest wall musculature or ribs/vertebrae immediately adjacent to the lungs.
- 3.1.3 Patients must have ECOG status of 0-3
- 3.1.4 Patients must have a life expectancy of at least 3 months as determined by the treating radiation oncologist.
- 3.1.5 Patients must have the ability to understand and the willingness to sign an IRB-approved informed consent document.

3.2 Exclusion Criteria

Prior radiation to any part of the body including the lungs or thorax is not an exclusion criteria

- 3.2.1 Tumor edge is greater than 2 cm from the chest wall. The edge of tumor is the edge of the gross tumor volume or GTV as defined in radiation treatment planning software. This is determined by the treating radiation oncologist.
- 3.2.2 Tumors that are expected to require more than 10 fractions of radiation as determined by the treating radiation oncologist.
- 3.2.3 History of using bone anti-resorptive agents including bisphosphonates or RANK-L inhibitors within the last 1 year.
- 3.2.4 Inability to stand or sit upright for at least 30 minutes, which is necessary for ingestion of risedronate.
- 3.2.5 Hypocalcemia defined as serum total calcium lower than 8.5 mg/dL on most recent bloodwork that is within 3 months of administration of study drug/placebo
- 3.2.6 Severe renal impairment (EGFR <30 mL/min) on most recent bloodwork that is within 3 months of administration of study drug/placebo
- 3.2.7 Known allergy to risedronate or other bisphosphonates

- 3.2.8 Surgery affecting the bone or dental operations within the last 6 months

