6.4 Duration of Follow-up

Follow-up for serious adverse events and mortality after the single dose of 150 mg of risedronate or placebo is administered will take place during the routine clinic visits during radiation treatment. Radiation treatments will occur within 1 – 3 weeks of taking the study drug. The 30 day follow-up window that is part of mandatory DSMC-SAE reporting will be considered 30 days from the end of all treatments of radiation. This visit can be either a phone call or a visit in person to review adverse events and may be conducted and documented in the medical record by either research study staff RNs or the treating physician. A window of +/- 7 business days is allowed for the 30 day followup assessment.

Specific toxicity related to radiation pneumonitis, radiation fibrosis, and chest wall pain will be collected at each followup point as per appendices K – M.

Patients removed from study for unacceptable adverse events will be followed until resolution or stabilization of the adverse event.

Patients will be followed for a minimum of 3 months for assessment of the primary objective.

Patients will be ideally followed in total for 12 months after completion of radiation therapy for the purposes of this study.

In the event that patients develop progressive disease or a new cancer, requiring additional chemotherapy they will be withdrawn from further study directed followup. In these situations, the followup schedules and imaging become dramatically different from what is directed on this protocol. Additionally further systemic chemotherapy treatments can heavily alter bone density/cortical thickness. As such, if patients develop new disease requiring additional systemic chemotherapy treatment outside of their initial SBRT, they will be withdrawn from study for further follow ups/study directed imaging. Any data that was collected prior to study withdrawal will still be used in analysis. **Immunotherapy or**

hormonal therapy for breast or prostate cancer will not be considered reasons for withdrawal.
Cryoablation or radiofrequency ablation will not be considered a reason for withdrawal from study.

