6.6 Study Calendar

	Baseline Prior to SBRT	Dosing (7- 21 days before SBRT)	During SBRT	1 month Post SBRT	3 ^f months post SBRT	6 ^f months Post SBRT	9 ^f months Post SBRT	12 ^f months Post SBRT
Informed consent	X							
Demographics Medical history History of diabetes Physical exam Performance status Vital signs Height, Weight, M ²		X						
Current Medications list	X				X			
Current or prior use of rank ligand inhibitors, bisphosphonates, and steroids with dates of use and dose as per Appendix G. ^h	X				X	X	X	X
CT chest with or without contrast	X ^a				X	X	X	X
Risedronate or placebo		X ^c						
Urine sample ^d	X				X	X	X	X
Serum Calcium EGFR Serum Creatinine Pregnancy test ^b		X						
Adverse event evaluation (Appendix E)					X			
Specific Radiation Related Chest wall Toxicity (Appendix K)				X ^e	X	X	X	X
Follow up phone call for assessment of adverse events without imaging (Appendix F)				X				
Fracture Incidence (Appendix Q)	X				X	X	X	X
Radiation Treatment Details (Appendix N)			X ^g					

^a Pre-SBRT CT chest scan will be the treatment planning scan. Fracture incidence will be assessed on CT scans

^b Urine pregnancy test (women of childbearing potential) performed within 1 week of treatment planning simulation for radiation.

^c Given once at 7 – 21 days prior to initiation of SBRT

^d For urine sample pick-up and transport, call [name] at [contact] (mobile), [contact] (office). If not available, call [name] at [contact] (mobile).

^e At the 30-Day time point this can be collected over the phone

^f Every 3 month follow-up, and CT imaging will have a window of +/- 8 wks

^g Appendix N may be completed during SBRT but should be completed within 12 weeks of completing SBRT

All pre-study activities must be completed within 12 weeks of the start of study drug including labs

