11.0 Statistical Considerations

11.1 Analysis of Primary Objective

The percent change in mean cortical thickness within regions receiving 30 Gy or more will be calculated from time of the treatment planning CT scan to 3 months post SBRT. This % change will be compared between the patients receiving risedronate and those receiving placebo.

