11.4 Power and Sample Size

Per analysis of our retrospective human data and preclinical data, we estimate that the mean cortical thickness for both cases and controls pre SBRT will be approximately 1.35 mm. At 3 months, in the absence of any treatment, we estimate approximately 16.7% loss of cortical thickness to bones to 1.13 mm (thus resulting in a mean change of 0.22 mm in controls) within the treatment field in regions of bone receiving ≥ 30 Gy. Conservatively, if risedronate use limits loss of cortical thickness by at least half on a percentage scale (i.e., expected cortical thickness at 3 months in treatment group 8.4% lower, or 1.24 mm, corresponding to an expected mean change in treatment group of 0.11 mm), and assuming a standard deviation of delta cortical thickness in both treatment and control patients of 0.20,⁴ then with a power of 0.80 and a one-tailed alpha of 0.05, we anticipate that we will need 42 patients per group to achieve desired power to illustrate significantly higher preservation of cortical thickness at 3 months post SBRT.

There is no human data to accurately estimate how significantly risedronate will limit bone loss following SBRT, however in our pre-clinical rodent models, cortical thickness was preserved in all mice receiving risedronate and in two mice cortical thickness increased. We have no mechanistic reason to suspect that risedronate would cause increased bone loss and therefore are utilizing a one-tailed alpha in our calculations.

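### Chemotherapy and steroid use at entry is permitted but enters no cortical-thickness analysis; prespecified adjustment would be a cheap, probably small, gain in precision

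*Combined protocol and SAP*

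**What the plan says.** **Entry.** Section 3.0 admits metastatic disease: "The lung tumor may be a lung primary tumor or a metastatic tumor to the lung". Among the exclusions in 3.2, the one that concerns drugs acting on bone is 3.2.3, "History of using bone anti-resorptive agents including bisphosphonates or RANK-L inhibitors within the last 1 year". Neither 3.1 nor 3.2 mentions chemotherapy, hormonal therapy or steroids.

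**After entry.** Section 6.4 withdraws patients who need additional chemotherapy for progression or a new cancer. It gives two reasons: follow-up and imaging schedules then depart from the protocol, and "Additionally further systemic chemotherapy treatments can heavily alter bone density/cortical thickness". Hormonal therapy for breast or prostate cancer is expressly not a reason for withdrawal.

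**Data collected.** The calendar in 6.6 has a current medication list at baseline and a separate row for "Current or prior use of rank ligand inhibitors, bisphosphonates, and steroids with dates of use and dose as per Appendix G", completed at baseline and at 3, 6, 9 and 12 months.

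**Analysis.** For the primary endpoint, section 11.1 says only: "This % change will be compared between the patients receiving risedronate and those receiving placebo". It names no test, model or covariate. Section 11.2.1 names repeated measures ANOVA for the later time points and dose bands, again without a covariate. Sections 4.0 and 10.0 describe randomisation without a stratification factor.

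**The concern.** The sponsor regards chemotherapy as a strong influence on the quantity the trial measures. When it starts after SBRT for new disease, that influence helps justify withdrawal. When it is already under way at entry, and may run through the 3-month CT, the plan does nothing with it. For steroids the documents are less direct: 1.2 lists glucocorticoid-induced osteoporosis among the indications, and 6.6 records steroid use with dates and dose, but no thickness analysis uses that record.

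Precision is at stake. Any thickness change caused by these exposures between the planning CT and the 3-month CT stays in the error term of a trial planned at 42 per group with almost no power to spare. Because 11.1 names no model, a visible imbalance between arms could be handled only by an adjustment chosen afterwards.

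**Working it through.** **Inputs from section 11.4.** Control loss: "thus resulting in a mean change of 0.22 mm in controls". Risedronate loss: "expected mean change in treatment group of 0.11 mm". The difference is 0.22 - 0.11 = 0.11 mm. The SD of change is 0.20 mm in both arms, with 42 per group, "with a power of 0.80 and a one-tailed alpha of 0.05". The check stays on the millimetre scale that 11.4 uses.

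**The plan's own figure.** Standardised effect = 0.11/0.20 = 0.55. A one-sided two-sample t-test needs 41.6, so 42 per group (41 by the normal approximation). The stated sample size reproduces. At 42 per group the standard error is 0.20 × √(2/42) = 0.0436 mm and power is 0.804.

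**Assumed inputs.** The documents do not say what share *p* of patients is exposed at entry, or by how much, *d*, exposure shifts the 3-month change. I take *p* = 10-30% and *d* = 0.05-0.11 mm, the upper value being as large as the whole target effect. I add *d* = 0.20 mm as an extreme.

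**Formulas.** A yes/no factor contributes variance *p*(1-*p*)*d*². As a share of the planned variance this is *p*(1-*p*)*d*²/0.04.

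- If the 0.20 mm SD already includes such patients, adjustment leaves a residual SD of √(0.04 - *p*(1-*p*)*d*²).
- If it does not, the unadjusted SD becomes √(0.04 + *p*(1-*p*)*d*²).

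| *p* | *d* (mm) | Share of variance | Residual SD (mm) | Adjusted power, SD includes them | Unadjusted power, SD excludes them |
|---|---|---|---|---|---|
| 0.10 | 0.05 | 0.6% | 0.199 | 0.805 | 0.802 |
| 0.10 | 0.11 | 2.7% | 0.197 | 0.813 | 0.794 |
| 0.20 | 0.11 | 4.8% | 0.195 | 0.820 | 0.787 |
| 0.30 | 0.11 | 6.4% | 0.194 | 0.826 | 0.782 |
| 0.30 | 0.20 | 21% | 0.178 | 0.878 | 0.735 |

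Adjusted power allows for two covariates (80 rather than 82 residual degrees of freedom). Worked example, row four: 0.3 × 0.7 × 0.11² = 0.00254; 0.00254/0.04 = 6.4%; √(0.04 - 0.00254) = 0.194.

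**Chance imbalance.** The SD of the difference in prevalence between arms is √(2*p*(1-*p*)/42). At *p* = 0.30 this is 0.10, which at *d* = 0.11 moves the arm difference by 0.011 mm. Its variance, 0.011² = 0.000121, divided by the squared standard error, 0.0436² = 0.0019, is again about 6.4%. Imbalance is therefore the same variance component seen from another side, not a second loss.

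**Cost if the factors are irrelevant.** With two covariates that explain nothing, power goes from 0.8036 to 0.8035.

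**The case against.** The case for leaving the plan alone has force in several places.

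- **The explicit statement covers chemotherapy only.** A reader might infer that the protocol says steroids and hormonal therapy also alter cortical thickness. It does not. Steroids appear through a labelled indication, androgen deprivation through a cited trial of bone mineral density at 2 years, and 6.4 keeps hormonal-therapy patients on study. This stands.
- **The asymmetry is partial.** One of the two withdrawal reasons in 6.4, the changed schedule and imaging, concerns disease arising after entry. The endpoint is change from the planning CT, so earlier bone loss is already in the baseline. Only extra loss over about 3 months can add noise. This stands and argues for small values of *d*.
- **Large gains need large assumptions.** A 0.20 mm shift would be 0.20/0.22 = 91% of the loss that 11.4 expects in untreated irradiated bone. Nothing in the documents supports that.
- **A reader might infer that the trial is underpowered, at about 0.73.** That needs both the extreme shift and an SD from patients without such therapy. Section 11.4 takes the SD from a cited retrospective series whose patient mix is not described.
- **Other covariates compete**, such as baseline thickness, bone dose, fractionation and prior thoracic radiation. This is true, and the wider gap is that 11.1 names no model. But chemotherapy is the one the sponsor itself singles out as a heavy influence.
- **Some absences cannot be confirmed.** The content of the Appendix G form and of the schema was not readable in the available text. It cannot be said that the form omits chemotherapy or that stratification is ruled out.

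None of this removes the narrower point: baseline data that are largely already collected on a recognised influence go unused, and using them costs almost nothing.

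**Conclusion.** The point holds as an inexpensive improvement, not as a flaw that threatens the result. Chemotherapy and steroid exposure at entry is allowed, and neither 11.1 nor 11.2.1 uses it. Over 10-30% prevalence and a 0.05-0.11 mm shift, with the 0.20 mm SD taken to include such patients, adjustment lifts power from 0.804 to about 0.805-0.826, a gain of roughly 0 to 2 percentage points. The figure of 0.88 belongs to the extreme 0.20 mm shift at 30% prevalence. All these gains rest on assumed inputs.

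A reader might go further and infer that the comparison is biased or that such patients should be excluded. The documents support neither. Randomisation makes exposure independent of arm in expectation, and the standard error already reflects chance imbalance. Whether 3.2 or the rationale in 6.4 should change is a clinical question; the two passages need to be reconciled.

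**What to change.** 1. In 11.1 and 11.2.1, prespecify a baseline-adjusted model that includes:
   - an indicator for systemic chemotherapy at the planning CT, with the time window that counts as exposure fixed before unblinding;
   - a separate indicator for systemic steroid use at the planning CT;
   - optionally, hormonal therapy as its own indicator, not pooled with steroids.
2. Code the indicators from the baseline medication record before unblinding.
3. Confirm that Appendix G captures chemotherapy dates, and add a line if it does not.
4. Report the unadjusted comparison as a sensitivity analysis.
5. Leave eligibility unchanged, and ask the sponsor to reconcile 3.2 with the rationale in 6.4.

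**Cost.** SAP wording, possibly one line on an existing form, and two degrees of freedom for the indicators (three with hormonal therapy). Two cost under 0.001 in power if the factors prove irrelevant.
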